### 12.2 Statistical Analysis Plan

Summary statistics will be used to describe the study population (such as ranges, medians of age, gender, baseline performance characteristics). The binomial and its exact 95% confidence interval will be used to estimate clinical response rate. A two-sided one-group chi-square test will be performed to detect a 50% response rate. Due to a small sample size, exact logistic regression may be used to evaluate the effect of baseline characteristics and other covariates with the clinical response. To evaluate inhibition of PDGF receptor, we will

correlate the presence or absence of c-kit and or PDGF-R mutations with clinical response to imatinib by performing chi-square tests or Fisher's exact tests. The cytokine/chemokine profile at baseline, 1 week and 4 weeks after of imatinib therapy will be analyzed using the proteomics approach. The concentration of each cytokine from the samples will be estimated. Friedman's test will be used to evaluate changes between time points with respect to cytokine levels. If a significant difference is detected, the Wilcoxon rank sum test will be used for pairwise comparisons. Exact logistic regression analysis will be used to detect any correlation between baseline concentrations and clinical responses. PK parameters including AUC,  $C_{max}$  and elimination half-life of imatinib will be estimated in the first 12 patients. PK parameters including AUC,  $C_{max}$  and elimination half-life of selected antiretrovirals may be estimated in selected patients. Summary statistics will be used to describe PK results. The incidence of specific AEs will be summarized by severity grade. The binomial proportion and its 95% confidence interval will be used to estimate the proportion of patients who experience an AE of severity Grade 3 or higher. The proportions of primary and secondary resistance to imatinib therapy will be estimated. Chi-square tests or Fisher's exact tests will be used to evaluate associations between c-kit and PDGF-R mutations with resistance to imatinib therapy.

Cluster analyses are planned for the real-time QPCR data. To evaluate the associations between single genes and response, categorical data analysis methods are proposed. If feasible, a multivariate model relating gene expression to response will be performed.

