## 12.0 STATISTICAL CONSIDERATIONS

### 12.1 Sample Size Estimation

The response rate (CR + PR) to imatinib in the pilot study is 50% to date. It is well known that some patients have regression of their KS after beginning HAART therapy. In order to minimize the effect of HAART being a potential confounding factor in response rates, recent studies have required patients on HAART to be on stable regimens for 12 weeks prior to initiation of treatment. Recent results from two placebo-controlled studies suggest as many 20% of responses in KS clinical trials may be delayed responses to HAART alone.[19, Walmsley, 1999 #136] Simon's two-stage design will be used to test the null hypothesis that the response rate (CR + PR) is 20% against the alternative that it is 50% at the one-sided 0.05 significance level with power of 0.90. Ten patients will be enrolled in the first stage. If no more than two patients respond, then the study will be stopped. If at least three patients respond, then the study will enroll up to a total of 22 patients. If no more than seven patients respond, the drug will be considered ineffective. If at least eight patients respond, the null hypothesis will be rejected in favor of the alternative hypothesis. The probability of early termination of the study is 0.68.

In our original estimate, we assumed a drop out rate of 10-15% based on our experience in the pilot study and calculated a sample size of 25 patients. However, we have had a higher drop out rate. Consequently, based on a drop out rate of 20-30%, we plan to roll a total of 30 patients to have 22 patients evaluable for response.

In the pilot study, we found that decreasing the dose of imatinib by 33% (600 mg/day to 400 mg/day) dramatically decreased the incidence of AEs. This dose reduction should reduce the steady state concentration of imatinib and its metabolite by 1 standard deviation of steady state plasma concentration, assuming constant clearance. This observation suggests a change in the plasma concentration imatinib and/or its metabolite of 1 standard deviation would be significant in our patient population. Based on this assumption, a PK sampling of 12 patients will provide a power of 88% to detect a 1 standard deviation change in the steady state level of imatinib and its metabolite with a type I error of 0.05 using a two-sided paired t-test.

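### Section 12.2 prescribes a two-sided chi-square on the primary endpoint without a null or level and without deferring to the Simon rule of 12.1; under conventional assumptions the two disagree at 8 of 22

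*Combined protocol and SAP*

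**What the plan says.** Section 12.1 (Sample Size Estimation) states the test in full: "Simon's two-stage design will be used to test the null hypothesis that the response rate (CR + PR) is 20% against the alternative". The response rate under that alternative is set at 50%, the level is one-sided 0.05 and the power is 0.90. The first stage has ten patients and the trial stops at two or fewer responders; otherwise it continues to 22. At the end, "If no more than seven patients respond, the drug will be considered ineffective", and "If at least eight patients respond, the null hypothesis will be rejected in favor of the alternative hypothesis". The stated probability of early termination is 0.68.

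Section 12.2 (Statistical Analysis Plan) handles the same endpoint in two sentences. The first is on estimation: "The binomial and its exact 95% confidence interval will be used to estimate clinical response rate". The second is on testing: "A two-sided one-group chi-square test will be performed to detect a 50% response rate". The testing sentence gives no null value, significance level or continuity correction. Its only number, 50%, is the alternative in 12.1. It does not mention the two-stage rule, and no other section ranks the two tests.

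**The concern.** The two tests differ in kind. The one in 12.1 is exact, one-sided and two-stage. The one in 12.2 is large-sample, two-sided and single-stage, with only 22 × 0.20 = 4.4 expected responders under a 20% null. Both are stated as things that will be done.

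The trouble would come at the smallest success that the design allows. A report that followed both sections could state that the null is rejected and, beside it, a chi-square p-value above 0.05. A borderline positive could then be described as negative, or the test could be chosen after the count is known. There is also a design cost if the chi-square were taken as decisive, because the trial was sized for the 12.1 rule.

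**Working it through.** **Inputs from 12.1:** n1=10, stop at ≤2; n=22, reject at ≥8; p0=0.20; p1=0.50; one-sided 0.05; power 0.90; early termination 0.68.

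**Assumptions for the 12.2 test, because the plan gives neither:** null 20% and two-sided 0.05. Alternatives are in step 5.

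**1. Reproduce the 12.1 design.**

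- Early termination = P(X1 ≤ 2 | 10, 0.20) = 0.678, stated as 0.68.
- P(reject) = Σ over x1=3..10 of P(X1=x1 | 10, p) × P(X2 ≥ 8−x1 | 12, p). At p=0.20 this is 0.0492; at p=0.50 it is 0.902.

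The design meets its stated level and power, and nothing in 12.1 needs changing.

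**2. Chi-square against 20% at n=22.** X² = (x − 4.4)² / (22 × 0.20 × 0.80) = (x − 4.4)² / 3.52 on 1 df. The corrected form uses (|x − 4.4| − 0.5)².

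| Responders | X² | p | X² corrected | p corrected | 12.1 rule |
|---|---|---|---|---|---|
| 7 | 1.920 | 0.166 | 1.253 | 0.263 | not rejected |
| 8 | 3.682 | 0.055 | 2.730 | 0.098 | rejected |
| 9 | 6.011 | 0.014 | 4.776 | 0.029 | rejected |

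At two-sided 0.05 the two tests agree at 7 and at 9 and differ at 8, with or without the correction. Above 9 both reject.

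**3. How often the design lands on 8 of 22.** P(pass stage 1 and total exactly 8) = P(reject with cut 8) − P(reject with cut 9). At 20% this is 0.0492 − 0.0188 = 0.030; at 50% it is 0.9022 − 0.8379 = 0.064. The same calculation gives 0.120 at 30% and 0.139 at 40%.

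**4. If the chi-square decided the trial.** The final cut would be 9 of 22. With stage 1 unchanged, alpha is 0.019 and power is 0.838, a loss of 0.902 − 0.838 = 0.064. False positives would fall.

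**5. Other readings of the 12.2 sentence.**

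- *Null 20%, two-sided 0.10.* This has the same upper tail as one-sided 0.05. At 8 of 22, 0.055 and 0.098 are both below 0.10; at 7 of 22, 0.166 and 0.263 are both above it. There is no conflict at 22.
- *Null 50%.* X² = (8 − 11)² / 5.5 = 1.636, p=0.20 (corrected 0.29). This asks whether the rate differs from 50% and does not address the 20% null.

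**6. The interval.** The exact two-sided 95% CI is 17.2% to 59.3% at 8 of 22 and 20.7% to 63.6% at 9 of 22.

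**The case against.** The strongest reply is that 12.1 already decides the trial. It names the test, null, level, sidedness and action at each count. The 12.2 sentence has no null, level or decision attached and can hardly act as a rival. Appendix XVI adds that stopping in phase II trials follows criteria stated in the protocol, although that covers stopping and not the final call. Much of this stands: a reader can reasonably infer that 12.1 governs. But 12.2 is the section headed as the analysis plan, it says the chi-square will be performed, and it never calls it supportive.

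It is also fair that two-sided 0.05 is stated nowhere for the response rate. The only level given for that endpoint is one-sided 0.05, and at the matching two-sided 0.10 the conflict at 22 disappears. That stands, and it limits the point. What remains is that the answer at 8 of 22 depends on a level the plan leaves out, and 0.05 is the usual default for a two-sided test.

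Three stronger readings are tempting, and the documents do not support them:

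- A reader might infer that the plan inflates false positives. With null 20% it does not; the 12.2 test is the stricter one at 0.05.
- A reader might take 50% as the null and conclude that most design successes would be contradicted. Failing to reject 50% does not contradict rejecting 20%; such results are compatible with the 12.1 alternative. The fair criticism is that the test would answer the wrong question.
- A reader might call the exact CI at 8 of 22 an error because it includes 20%. Section 12.2 uses that interval for estimation, and a two-sided 95% interval can include a value that a one-sided 0.05 test rejects.

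**Conclusion.** The point holds as a defect in the link between the two sections. Section 12.2 prescribes a test of the primary endpoint that does not match the decision rule in 12.1, lacks a null and a level, and is not ranked below it. The 12.1 design itself is sound.

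On the assumed null of 20% and two-sided 0.05, the effect is confined to exactly 8 of 22, with a probability between 0.030 and 0.139 over true rates of 20%, 30%, 40% and 50%. The drop in power to 0.838 applies only if the chi-square were treated as the deciding test, which the documents do not say. At two-sided 0.10 the conflict at 22 vanishes.

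It should be fixed: the affected result is the one where it matters most which test governs, and the repair costs almost nothing.

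**What to change.** In 12.2, replace the chi-square sentence with: *The null hypothesis of 20% will be tested by the two-stage rule of Section 12.1 (reject if at least 8 of 22 evaluable patients respond; exact one-sided alpha 0.049), and the two-stage one-sided p-value will be reported.*

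Alternatively, keep the chi-square as a supportive analysis only, with the null stated as 20%, a level that matches the one-sided 0.05 of 12.1, and the choice on continuity correction stated.

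In either case add: *The exact two-sided 95% confidence interval is descriptive and does not decide the test.*

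A two-stage one-sided lower bound beside that interval is optional. A rule for a final evaluable number other than 22 is a separate point (12.1 says "we plan to roll a total of 30 patients to have 22 patients evaluable for response") and is not needed for this repair.

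The cost is about two sentences of wording, with no extra patients or data.

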#### 1.2.2.1 Receptor Mutation Analysis

Mutations of c-kit and PDGF-R have been shown to play a role in tumorigenesis and imatinib resistance. Activating mutations of c-Kit have been reported in mastocytosis, acute myelogenous leukemia, GISTs, myeloproliferative disorders (MPD) and sinonasal lymphomas. In vitro studies suggest activating mutations in the kinase domain of c-Kit are resistant to inhibition by imatinib. Additionally, activating mutations in the kinase domain of PDGF-R  $\alpha$  have been reported in GISTs. We will correlate the presence or absence of c-Kit and/or PDGF-R mutations with clinical response to imatinib.

As the experience with imatinib therapy for CML increased, it became clear that some patients who initially responded later relapsed. Studies demonstrated multiple mechanisms of resistance including over-expression of BCR/ABL transcripts, acquisition of new chromosomal abnormalities and mutation of the kinase domain. In one study, mutations of the kinase domain appeared to be the mechanism of resistance in 23 of 43 cases. At the time of discontinuation, we will biopsy a lesion that is clearly growing or has not responded and sequence PDGF-R and c-Kit.

If any novel mutations are found in either of these cases, we will determine in vitro whether they are activating mutations and/or resistant to imatinib.

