### **2.2 Secondary Objectives**

2.2.1 Evaluation of inhibition of PDGF receptor as determined by immunohistochemistry.

2.2.2 Evaluation of cytokine profiles pre and post imatinib therapy.

2.2.3 Evaluation of pharmacokinetic profile of imatinib and antiretrovirals in HIV patients.

2.2.4 Evaluation of mechanisms of primary and secondary resistance to imatinib therapy.

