- 4.2.6 Biologic Endpoints - Biopsies will be performed at baseline (two), at Day 8 and at time of progression. One biopsy will be performed at baseline and at time of progression or treatment discontinuation for receptor mutation analysis. The DNA from these biopsies will be used to assess exons 12 and 18 in PDGDR  $\beta$ , and exons 11 and 17 in c-kit for mutations that may activate the target receptors or confer resistance to imatinib. If mutations are now found in these exons, we will sequence other exons in which activating mutations have been described. Additionally, RNA from these biopsies will be stored for sequencing cDNAs and accessing expression of downstream targets. These biopsies will be fresh biopsies stored in RNAlator storage media (see Appendix X). Two more biopsies will be performed at baseline and on Day 8 for receptor phosphorylation. These biopsies will assess inhibition of PDGF receptor and will be performed on each specimen. These biopsies will be fixed in 10% formalin (see Appendix X). Serum and plasma specimens for cytokine profiles will be taken at baseline, Day 8 and Day 29 (see Appendix XI). DNA and RNA from PBMCs in these specimens will be stored. The DNA will be used to determine if PDGF-R and c-kit mutations are present in circulating PBMCs, which are infected with KSHV or are restricted to the KS lesions. The RNA will be used for accessing the effect of PDGF-R and c-kit inhibition on the expression of cytokines and other potential downstream targets.
- 4.2.7 Pharmacokinetics - The first 12 patients will have PK sampling performed on Days 1 and 15. Samples will be collected on both days on the following schedule: 0 (immediately prior to patient taking meds for that day), 0.5, 1, 2, 3, 4, 8 and 24 (immediately prior to the next day's dose) hours (see Appendix XII). These data will be compared with historical PK data acquired at the same time points in normal volunteers.

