## **APPENDIX X: PUNCH BIOPSY**

### **RECEPTOR MUTATION ANALYSIS**

#### **A. METHODOLOGY**

Each patient will have a 4 mm punch biopsy performed at baseline and at the time of progression or treatment discontinuation of a representative lesion. RNA and genomic DNA will be isolated from samples. PCR primers for the genomic DNA were designed to begin in the flanking introns and cover the entire exon being studied. The PCR products will be gel purified and will then be subcloned into PCR4blunt-TOPO vector. The ligated vectors for each exon will then be used to transform competent E. Coli XL1 blue and the bacteria will be plated and grown overnight. Single colonies will be picked and then mini-prepped. The DNA from the mini-preps will be sequenced. Because the malignant cells of KS will only be a portion of the biopsy, the heterogeneity of the tumor must be taken into account before we can declare a negative result. Based on our previous studies we estimate that approximately 50% of a 4 mm punch biopsy is composed of KS spindle cells which express PDGF-R  $\beta$  and c-kit. If only one allele of the KS spindle cell has a mutation and the ratio of normal to mutant cells is one to one, only one out of four exons carry the mutation. To calculate the number of sequences to perform on each exon to assure a mutation was not missed, we first decided level of 95% confidence level was acceptable. The number of assays required is the number of times the negative result (normal sequence) must happen to be less than or equal to 5% (100% -95%). Mathematically this can be solved as a probability problem.

$$(p \{\text{normal sequence}\})^n < 0.05 \quad \text{where } n \text{ is number of assays and } p(\text{normal sequence}) = 0.75$$

$$\text{This transforms to } (0.75)^n < 0.05 \rightarrow n \log(0.75) < \log(0.05) \rightarrow n(-0.125) = -1.301 \\ n = 10.41 \rightarrow 11$$

Thus to achieve a 95% confidence of not missing a mutation each exon will be sequenced 11 times. If a positive mutant clone is discovered, it is possible that the mutation is an error introduced by PCR. We are using PFU polymerase, which has a lower mistake rate than Taq polymerase to reduce the incidence of mistakes. Because PFU still has a mistake rate of 1 in 10,000 nucleotides all mutants will have to be confirmed by two more clones from different PCR reactions to be considered a positive result. If mutations are present, we will determine if they correlate with non-response.

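### Section 12.2 evaluates PDGF-R inhibition through mutation status, which does not measure inhibition, and neither it nor Appendix IX plans a confidence interval for the proportion inhibited or a paired comparison of scores

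*Combined protocol and SAP*

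**What the plan says.** Section 2.2 lists as a secondary objective: "Evaluation of inhibition of PDGF receptor as determined by immunohistochemistry". Sections 1.2.1 and 4.2.6 assign this to phosphorylation staining of biopsies taken at baseline and Day 8.

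The corresponding sentence in Section 12.2 opens "To evaluate inhibition of PDGF receptor, we will" and continues "correlate the presence or absence of c-kit and or PDGF-R mutations with clinical response to imatinib by performing chi-square tests or Fisher's exact tests". This is almost the same statement as in Section 1.2.2.1, the receptor mutation analysis: "We will correlate the presence or absence of c-Kit and/or PDGF-R mutations with clinical response to imatinib". Later in 12.2, mutations appear again, this time for resistance: "Chi-square tests or Fisher's exact tests will be used to evaluate associations between c-kit and PDGF-R mutations with resistance to imatinib therapy".

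The IHC analysis is in Appendix IX. Under A.3, two blinded pathologists score staining from 0 to 5+, and the final score for a sample is an average over four sections. Under A.4, scores of 0 to 2+ are low and 3+ to 5+ are high. A pair that goes from high to low is inhibited, a pair that stays high is not, and pairs low at baseline are left out. One chi-square test relates the seven-day result to clinical response, and the association is stated as an a priori hypothesis.

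**The concern.** The one sentence in the analysis section that names inhibition describes an analysis of something else. Genotype against response cannot show whether the receptor was less phosphorylated at Day 8 than at baseline. A statistician working from 12.2 alone would report a mutation table under objective 2.2.1 and could overlook the IHC pairs.

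Appendix IX supplies an IHC analysis, but its only planned test asks whether inhibition predicts response. How often the receptor is inhibited, and how far the score falls, get no planned interval or test. The association test also depends on having some pairs that are not inhibited, so it may fail when the drug reaches its target in nearly everyone.

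**Working it through.** The documents give no sample size, power or precision for this endpoint, so there is no figure to reproduce. The check is a comparison of texts, followed by illustrative arithmetic.

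**1. What each analysis measures**

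| | Objective 2.2.1 | 12.2 sentence on inhibition | Appendix IX A.4 |
|---|---|---|---|
| Measure | IHC | c-kit/PDGF-R mutation present or absent | IHC phosphorylation score, high or low |
| Biopsies | Baseline and Day 8 (4.2.6) | Baseline and progression or discontinuation | Baseline and Day 8 |
| Result | Inhibition | Association with response | Association of inhibition with response |

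The mutation biopsies are separate specimens. Section 4.2.6 says "One biopsy will be performed at baseline and at time of progression or treatment discontinuation for receptor mutation analysis", and Appendix X agrees: "Each patient will have a 4 mm punch biopsy performed at baseline and at the time of progression or treatment discontinuation". None is taken at Day 8.

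**2. What 12.2 plans elsewhere**

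It plans binomial confidence intervals for clinical response and for Grade 3 or higher adverse events, and Friedman's test for cytokine changes over time. It has no counterpart to either for the IHC pairs.

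**3. When the A.4 test cannot be computed**

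If each of n usable pairs is inhibited independently with probability q, the chance that all are inhibited is q^n. Both n and q are assumptions.

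- n = 7 and 9 apply the pilot yield in 1.1.5 (three of ten patients with an evaluable pair shown active at baseline): 22 × 3/10 = 6.6 and 30 × 3/10 = 9.
- n = 18 applies the pilot's baseline evaluability (six of ten): 30 × 6/10.
- n = 22 is the planned number evaluable for response in 12.1. Nothing in the documents caps the pairs at that number.

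| Pairs | q = 0.75 | q = 0.80 | q = 0.90 | q = 0.95 |
|---|---|---|---|---|
| 7 | 13.3% | 21.0% | 47.8% | 69.8% |
| 9 | 7.5% | 13.4% | 38.7% | 63.0% |
| 18 | 0.6% | 1.8% | 15.0% | 39.7% |
| 22 | 0.2% | 0.7% | 9.8% | 32.4% |

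**4. What the proportion would still give**

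When all n pairs are inhibited, the exact lower 95% limit is 0.025^(1/n): 0.590 for 7 of 7 and 0.815 for 18 of 18. Mid-range results are imprecise: 5 of 9 gives 21% to 86%, and 9 of 18 gives 26% to 74%.

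**5. What the pilot says about q**

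Section 1.1.5 reports four evaluable pairs, of which three showed activation at baseline and inhibition after treatment. The fourth is not described. The exact 95% interval for 3 of 4 is 19% to 99%.

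**6. Gaps in the scoring rule**

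A.3 and A.4 do not say how the two pathologists' scores are combined or where an average between 2 and 3 falls. Assuming whole-unit section scores, averaging four sections gives 21 possible values from 0 to 5, of which 3 lie strictly between 2 and 3. Averaging eight readings gives 41, of which 7 do. Ordinary rounding would leave only 2.5 open.

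**The case against.** The strongest reply is that the protocol already covers the objective. Appendix IX specifies blinded scoring, a cut, a definition of inhibition, an exclusion rule, a hypothesis and a test. The number inhibited can be read from the margin of that table, and the mutation correlation is itself planned in 1.2.2.1. On this view, what remains is a misplaced sentence and a missing cross-reference for a secondary endpoint.

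Much of this stands. A reader of 12.2 alone might infer that the IHC objective has no analysis; Appendix IX shows that it has one. The misplaced sentence still assigns the wrong analysis to a named objective, and a count without an interval or paired test leaves inhibition itself without planned inference.

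Three other stronger readings are not supported:

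- **That the pilot showed inhibition in all active pairs.** A reader might infer 3 of 3. The fourth pair may have been inactive, active but not inhibited, or active for only one marker, so the rate is open.
- **That few pairs will be usable.** The 7 to 9 scenario borrows a 4-week yield. Section 1.2.1 says spindle-cell loss at 4 weeks reduced the staining population and moved the biopsy to Day 8 for that reason. That scenario is the low end.
- **That the low/high cut must be replaced.** The pilot used a tyrosine 751 antibody at 4 weeks, and this trial uses tyrosine 783 at Day 8. That is a caution about the cut, but the documents offer no better basis for another, so it may stay.

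The formalin sentence in 4.2.6, "These biopsies will be fixed in 10% formalin (see Appendix X", points to the mutation appendix. It is incomplete more than wrong, because the shared biopsy log at the end of Appendix X also lists the formalin phosphorylation specimens.

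**Conclusion.** The point holds as a secondary-endpoint correction that should be made. Section 12.2 states a purpose and gives an analysis that cannot serve it. The analysis that can serve it sits in an appendix 12.2 does not cite, and neither place plans an interval for the proportion inhibited or a comparison of the paired scores.

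The first part rests on the text alone. The size of the risk to the A.4 test rests on assumed pair numbers and inhibition rates: it is substantial with few pairs and a high rate, and negligible with 22 pairs at 75%. The pilot does not settle which applies.

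A reader might infer that the trial's main conclusion is at risk. It is not: the response rule in 12.1 uses none of these data. Nor is there reason to demote the inhibition-response association to exploratory, since Appendix IX states it as an a priori hypothesis.

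**What to change.** In 12.2, replace the sentence on inhibition with text to this effect:

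> PDGF-R inhibition (objective 2.2.1) is defined from the paired IHC scores in Appendix IX. The proportion inhibited among pairs high at baseline will be given with an exact 95% CI. The baseline-to-Day-8 change in score in all evaluable pairs will be tested with the Wilcoxon signed-rank test. The a priori association of inhibition with response will be tested as in Appendix IX A.4, with Fisher's exact test when expected counts are small.

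Then:

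- Move the mutation-response correlation under objective 2.2.4, beside the mutation-resistance sentence already in 12.2.
- In Appendix IX, state that leaving out baseline-low pairs applies only to the inhibited/not-inhibited classification and its association with response, not to the paired score comparison.
- In Appendix IX, replace the reference to Aims 2 and 3, which this protocol does not contain, with the objective numbers.
- In Appendix IX, fix one rule for combining the two readers and for averages between 2 and 3 before scores are linked to response.
- In 4.2.6, add Appendix IX to the reference for the phosphorylation biopsies.

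**Cost.** Section 13.2 requires a written amendment approved by Novartis, CTEP and the Investigator, and Sections 13.1 and 13.2 add IRB approval if the change is judged significant. The amendment would apparently fall mid-trial, since 12.1 already reports higher drop-out than assumed. No new biopsies or readings are needed.

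**Limits of the new analyses.**

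- The proportion will be imprecise.
- Fisher's test has little power in lopsided splits. With one non-inhibited pair its smallest two-sided p is 1/n: 1/8 = 0.125 for a 1/7 split, and below 0.05 only from 21 pairs (1/21 = 0.048).
- The signed-rank test has smallest two-sided p of 2/2^n, so it needs at least 6 non-zero differences (0.031, against 0.063 with 5).
- Baseline-low pairs have little room to fall and will dilute the paired change.
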